5.2 Pragmatic cluster randomised controlled trial

We will conduct a pragmatic, three-arm 1:1:1 parallel group, cluster randomised controlled superiority trial in Tanzania over a 12-month period. Following the pilot in India, a decision was taken to remove one of the intervention arms, and conduct a two-arm 1:1 parallel group, cluster randomised trial in India. Cluster unit is the facility providing primary care services, with randomisation to one of the following groups:

- Pulse oximetry plus CDSA (Tanzania only)
- Pulse oximetry with paper job aid based on IMCI (or national guidelines) incorporating pulse oximetry
- Control (routine care, with refresher training)

Sick children 0 – 59 months of age will be managed by healthcare providers according to which intervention the facility they attend have been assigned (see 6.3 for further detail).

As the intervention targets healthcare provider practice, we have opted for a cluster design at the facility level to: avoid contamination that would occur if randomisation occurred at the

individual level; avoid introducing different processes within one facility; and enable evaluation of effectiveness in real-world settings.

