8.3.1 Pragmatic cluster RCT

Analyses will follow CONSORT guidelines and intention-to-treat principles, including all participants as randomized. A flowchart will describe the inclusion and follow-up of participants by study arm.

Baseline characteristics will be described by study arm with summary statistics such as median and interquartile range or number and percentage; no formal testing between arms will be performed. Outcomes will be described by arm using summary statistics. The two primary outcomes, the proportion of children with a severe complication and the proportion of children appropriately hospitalized, will be assessed using a random effects logistic regression models with the cluster included as a random effect. Results will be reported with odds ratios, risk differences and 95% confidence intervals (CI). Binary secondary outcomes will be evaluated in the same way. Continuous secondary outcomes will be assessed using random effects linear regression models, reporting adjusted mean differences between arms with 95% CIs.

All models will be adjusted for randomization stratification factors and any baseline variables found to be randomly imbalanced across arms. Assessment for imbalances between baseline variables will be by visual inspection only; there will be no formal testing of baseline characteristics across randomized groups.^{53,54}

For the analysis of the primary endpoints, we will use a hierarchical fallback procedure, which is a closed test procedure using a weighted Bonferroni.^{55,56} This method recycles unspent significant levels to test subsequent hypotheses with a pre-specified hypothesis sequence.⁵⁷ This uses alpha propagation making it more powerful than the Bonferroni method.

The primary outcomes will be evaluated according to hierarchy of importance as follows:

H_1 : There is no difference between the experimental arm and control arm with respect to severe complications by day 7

H_2 : There is no difference between the experimental arm and control arm with respect to hospital admissions within 1 day of the primary consultation

First, we would test the null hypothesis H_{12} which is that neither H_1 nor H_2 are significant. We would reject the null hypothesis of H_{12} if either $p_1 \leq \alpha_1$ or $p_2 \leq \alpha_2$ where α is equally distributed between the endpoints i.e. $\alpha_1 = 0.025$ and $\alpha_2 = 0.025$.

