3.2 Randomisation

The allocation sequence was generated separately for each country, stratified by facility type (dispensary/health center) and location (urban/rural) in Tanzania; by facility type (primary healthcare centres (HC)/community health centers) and district (Deoria, Sitapur, Unnao) in India. The target number of facilities were randomly selected from all eligible facilities and allocated to the trial arms. The remaining eligible facilities were retained in a back-up list for later allocation (using the same procedure) should the need arise (e.g. in case of facility exclusion at study start, or in case of need to add additional clusters in the event of recalculation of sample size). Given the cluster design, concealment will occur only at the stage of allocation of facilities, which will be conducted centrally and distributed to study sites. Participants will receive the intervention based on the facility they attend.

The allocation sequence generation was carried out by a statistician, independent from the study, prior to the recruitment of the first patient.

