3.4 Sample Size

The sample size for the pragmatic RCT is calculated separately for each country, based on the following assumptions:

- ξ power of 80%
- ξ alpha level of 0.05 per arm
- ξ intra-cluster correlation coefficient (ICC) of 0.001
- ξ 1.1% severe complications in the control arm
- ξ 1.5% appropriate hospitalisations (within 24 hrs of Day 0 and as a results of referral) in the control arm

In India, initial sample size calculation for the three arm trial was based on having the power to detect a 30% or greater decrease in severe complication and 30% or greater increase in appropriate hospitalisation for each arm compared to control with 40 cluster per arm. This assumes average recruitment of 510 children per cluster over the 12 month period (total 40800), with an average of 110 per CHC per month and 20 children per PHC, assuming an average facility ratio CHC : PHC of 1:3. Following the decision, based on the pilot, not to introduce the CDSA, facilities were reallocated to the remaining two arms up to 60 facilities per arm.

In Tanzania, the study would have the power to detect a 30% or greater decrease in severe complication and a 30% or greater increase in appropriate hospitalisation for each arm compared to control with 22 clusters per arm. This assumes average recruitment of 1680 children per cluster over the 12 month period (total 110880), with an average of 350 children per health centre per month and 70 children per dispensary per month, assuming an average facility ratio health center : dispensary of 1:3.

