4.3 Analysis Populations

All analyses will follow the intention to treat (ITT) principle, retaining facilities and participants in their initially randomised groups irrespective of the intervention received or any protocol violations. However, clusters provided from the start of the trial with a different intervention package than the one they were randomised to will be analysed according to the arm of the intervention they delivered.

A complete case set will also be defined, including only participants whose follow-up information are available (i.e. at least one follow-up was conducted). Analysis of the primary outcomes will be performed on both the ITT and the complete case set for final analysis and analyses for the DMC review.

No safety set will be defined but safety information will be reported overall and by use of intervention as defined in section 4.2.

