6.1.2 Health, hospitalisation and referral outcomes

6.1.2.1 Proportion of children with a severe complication by Day 7

Severe complication is defined as death or secondary hospitalisation. Secondary hospitalisation refers to any delayed hospitalisation (occurring at any point greater than 24hrs after the Day 0 consultation) and any hospitalisation occurring without a referral.

Information on death and hospitalisation will be taken, in order, from:

- ξ Day7 follow-up assessment
- ξ If Day7 follow-up assessment is missing, Day28 follow-up assessment

Death will be counted in the numerator if death date is within 7 days of Day0 (7th day included). Hospitalisation will be counted in the numerator if the child was not referred at Day0 or hospital admission date is within 7 days of Day0 (7th day included) but after 24hrs of Day0.

The denominator will be all children recruited. Children for whom no death and hospitalisation data are available or withdrew prematurely from the study will be assumed to be alive and not hospitalised by Day7.

6.1.2.2 Proportion of children with a severe complication by Day 28

Severe complication is defined as per the outcome above.

Information on death and hospitalisation will be taken, in order, from:

- ξ Day7 follow-up assessment
- ξ If Day7 follow-up assessment is missing or no outcomes were reported, Day28 follow-up assessment
- ξ If both Day7 and Day28 assessments are missing or no outcomes were reported, unscheduled visits (deaths only)

Death will be counted in the numerator if death date is within 28 days of Day0 (28th day included). Hospitalisation will be counted in the numerator if the child was not referred at Day0 or hospital admission date is within 28 days of Day0 (28th day included) but after 24hrs of Day0.

The denominator will be all children recruited. Children for whom no death and hospitalisation data are available or withdrew prematurely from the study will be assumed to be alive and not hospitalised by Day28.

6.1.2.3 Proportion of children admitted to hospital within 24 hours of Day 0 consultation and as a result of a referral

Information on hospitalisation will be taken, in order, from:

- ξ Day7 follow-up assessment
- ξ If Day7 follow-up assessment is missing, Day28 follow-up assessment

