6.2 Analysis Methods

6.2.1 Analytical Methods

Outcomes will be described by arm using summary statistics. In particular, counts and percentages will be used for binary variables and reported with one decimal place; mean and standard deviation (SD) or median (IQR) for continuous variables depending on their distribution. Mean and median will be displayed with one decimal place and SD and IQR will be presented with two decimal places.

The two primary outcomes will be assessed using a random effects logistic regression model with the cluster included as a random effect. If convergence issues arise due to sparse data, clusters may be dropped or combined to higher grouping level (e.g. district).

Results will be reported with odds ratios, risk differences and their associated 95% confidence intervals (CI). The control arm will be used as reference category.

Secondary outcomes and other binary outcomes of interest will be evaluated in the same way.

Other continuous outcomes of interest will be assessed using random effects linear regression model with the cluster included as a random effect. Results will be reported in terms of adjusted mean differences between arms with associated 95% CIs.

Modelling of secondary outcomes will be performed if numbers allow.

For interim analyses and DMC analyses, only the two primary outcomes will be presented. Modelling will not be performed and results will be reported in terms of summary statistics only.

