6.2.3 Test of Assumptions, Actions to be taken

Continuous variables will be inspected using histograms: 1) to assess for outliers which may be queried for accuracy, and 2) to assess whether appropriate transformations are required for analyses.

As a multilevel logistic regression model is estimated using quadrature (rather likelihood methods), a quadrature check to test for adequate model fit will be performed. In case of unreliable model fit, generalised estimating equations will be used to fit the model which will provide population-averaged odds ratios and 95% confidence intervals.

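### SAP 6.2.1 lets randomised facilities be dropped, or merged to district, if a sparse-data model does not converge: dropping breaks intention to treat, one reading of merging loses the facility-level correction, and no order of fallbacks is fixed

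*SAP*

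**What the plan says.** The randomised unit is the facility. Protocol 5.2: "Cluster unit is the facility providing primary care services". SAP 6.2.1 fits a logistic model with the cluster as a random effect to both primary outcomes, and says that secondary and other binary outcomes are handled likewise, with modelling of secondary outcomes only if numbers allow. For non-convergence it says: "If convergence issues arise due to sparse data, clusters may be dropped or combined to higher grouping level (e.g. district".

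Three statements bear on dropping:
- Protocol 8.3.1: "Analyses will follow CONSORT guidelines and intention-to-treat principles, including all participants as randomized".
- SAP 4.3, for all analyses: "retaining facilities and participants in their initially randomised groups irrespective of the intervention received or any protocol violations". Its one exception is for clusters given a different intervention package from the start of the trial.
- SAP 6.1.2, for both primary outcomes: "The denominator will be all children recruited".

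On combining, SAP 3.2 shows that district is a randomisation stratum in India: "by facility type (primary healthcare centres (HC)/community health centers) and district (Deoria, Sitapur, Unnao) in India".

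SAP 6.2.3 has a second fallback, triggered by a failed quadrature check: "In case of unreliable model fit, generalised estimating equations will be used to fit the model which will provide population-averaged odds ratios". It names no cluster level and does not refer to 6.2.1.

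**The concern.** The sentence offers two discretionary actions. It does not say which clusters are affected, by what criterion, in what order, or what combining means.

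Dropping removes every child recruited at a randomised facility, which the protocol and the rest of the SAP rule out.

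Combining has more than one meaning. If district becomes the random effect, the model no longer represents variation between facilities. An Indian district contains both arms, so a district effect cancels from the arm comparison and cannot stand in for the facility effect. If facilities are instead merged into district-by-arm groups, six units remain in India, and the result depends on the reference distribution, which the SAP does not give.

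Two analysts following the SAP could therefore report different p-values from the same data, and the route could be chosen after the data are seen.

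**Working it through.** **Inputs.** From SAP 3.4: ICC 0.001; control risk of severe complication 1.1%, falling by 30% to 0.77%; 110 children a month per CHC and 20 per PHC, ratio 1:3. Over 12 months that is 1,320 and 240, mean 510. From SAP 4.1: 2.5% per primary outcome. Assumptions: 60 facilities per arm (the SAP says "facilities were reallocated to the remaining two arms up to 60 facilities per arm"), taken as 15 CHCs and 45 PHCs split equally over three districts; two-sided tests; half and quarter recruitment as illustrations of sparser data.

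**The plan's own figure.** Two proportions, 1.1% v 0.77%, 80% power, two-sided 5%: 13,351 per arm. Design effect 1 + 0.001 × (510 − 1) = 1.509. 13,351 × 1.509 ≈ 20,147, and 20,147/510 = 39.5, so 40 clusters. The stated Indian figure reproduces.

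**District replaces facility.** If facility variation is ignored, the error is 2Φ(−2.241/√DE), with DE = 1 + 0.001 × (m − 1). Taking m as the mean gives a lower figure. Taking m as the size-weighted mean, (15 × 1,320² + 45 × 240²)/30,600 = 939, allows for unequal sizes.

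| Recruitment | DE (mean / weighted) | Formula error | Simulated, district as random effect | Simulated, facility as random effect |
|---|---|---|---|---|
| Planned | 1.51 / 1.94 | 6.8% / 10.7% | 10.3% | 3.0% |
| Half | 1.25 / 1.47 | 4.5% / 6.4% | 5.8% | 3.6% |
| Quarter | 1.13 / 1.23 | 3.5% / 4.4% | 4.0% | 3.0% |

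The simulations use 2,000 beta-binomial trials per setting and a Wald z test (Monte Carlo standard error 0.4 points at 3%, 0.7 at 10%). A separate check with the facility correction removed gave 11.0%, 6.4% and 4.0%.

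**District-by-arm groups.** A Wald z test from the random-effects model rejects in 9.3%, 5.4% and 3.8% of null trials at planned, half and quarter recruitment. A t test on 4 degrees of freedom over the same six groups stays near 2.5% (2.7% in one check, 2.5% in another, at planned recruitment), but power for 1.1% v 0.77% is then about 45%, against 87% for the facility model.

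**Dropping.** The SAP gives no criterion; that facilities with no events would go is an inference from its reference to sparse data. The beta-binomial probability of no event in a 240-child PHC is 9.3% at 1.1% and 19.0% at 0.77%. Expected losses are 45 × 0.093 = 4.2 control and 45 × 0.190 = 8.6 intervention facilities. Events are unchanged and denominators shrink:
- control: 30,600 × 0.011 = 336.6 events in 30,600 − 4.2 × 240 ≈ 29,600 children, 1.137%;
- intervention: 30,600 × 0.0077 = 235.6 events in 30,600 − 8.6 × 240 ≈ 28,540 children, 0.826%.

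The odds ratio moves from 0.70 to about 0.72 (0.73 as the mean of fitted models), towards no effect. There is no bias under the null. Simulated power falls from 87% to 78%.

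**How likely is the trigger?** Expected control-arm events in India are 60 × 510 × 0.011 = 337, or 224 with 40 facilities. In Tanzania a dispensary of 70 × 12 = 840 children has no severe complication with binomial probability below 0.2% even at 0.77%.

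**The case against.** The strongest reply is that the inflation is largest where the clause is least likely to be used. The trigger is sparse data, inflation grows with cluster size, and as the data thin out the district figure falls to about 4% against 3%. That stands. A reader might infer that the primary result carries a threefold false-positive risk. The documents do not support that, because with about 337 expected control events the primary models should converge.

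A reader might also infer that every form of combining inflates error. It does not. For district-by-arm groups, inflation comes from a z test on six units, and the SAP names no reference distribution. The most direct reading of the sentence may be that only sparse facilities are merged with others in the same arm. Simulated for zero-event facilities, that gives a null rejection rate of 2.1% at planned recruitment, so no inflation; power is 80% against 87%.

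Nor does dropping appear to bias the result materially: the shift is small and towards no effect.

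Finally, 6.2.1 and 6.2.3 can be read as successive steps, the first for a model that will not fit and the second for one that fits but fails its check. Neither section says so, and on that reading dropping or combining would still come before GEE.

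What survives is the contradiction over dropping, the undefined meaning of combining, and the missing order and cluster level.

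**Conclusion.** The concern holds, at minor to should-fix. Dropping a randomised facility conflicts directly with protocol 8.3.1, SAP 4.3 and the stated denominators, whatever its numerical effect. Replacing facility by district loses the facility-level correction in India, with error of about 10–11% at planned recruitment, 6% at half and 4% at a quarter, at nominal 2.5%. District-by-arm merging gives either about 9% error at planned recruitment (z test) or about 45% power (t test on 4 df).

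These figures rest on ICC 0.001, 60 Indian facilities per arm, the planned facility sizes and an equal split over districts. The clause matters mainly for sparser outcomes evaluated in the same way, and for young-infant results if those are modelled. No size of effect has been shown for these.

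**What to change.** Delete the drop-or-combine sentence in SAP 6.2.1 and state one ordered fallback there, with 6.2.3 referring to it. Suggested text:

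*All randomised facilities are retained, including those with no events. If the random-effects model does not converge or the quadrature check fails, it is refitted with other quadrature points or optimiser settings; if this fails, GEE with facility as the cluster and small-sample-corrected robust standard errors is used.*

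Add that district (India) or urban/rural location (Tanzania) stays a covariate and never replaces facility as the cluster. If a facility-level summary analysis is kept as a last resort, specify facility proportions on the risk-difference scale, which is defined for facilities with no events, and state the weighting.

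In a check under the Indian assumptions, facility-clustered GEE with a small-sample correction gave error of 3.2%, 3.0% and 2.6% at planned, half and quarter recruitment. The cost is SAP wording only; the protocol and data collection do not change. The downside is that GEE gives a population-averaged odds ratio, which 6.2.3 already accepts.

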6.2.2 Adjustment for Covariates

All models will be adjusted for stratification factors (facility type, location) and baseline variables that are found to be randomly imbalanced across arms. As described in Section 5.5, the imbalance will only be assessed visually and without performing any formal comparison.

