6.1.2 Tanzania

Setting

Three councils (Sengerema District Council in Mwanza region, Tanga City Council in Tanga region and Kaliua in Tabora region)

Tanzania under-5 mortality rate: 53 / 1000 live births⁴⁴

Facilities

Dispensaries and health centres (HCs)

Services

Dispensaries offer services such as immunization, family planning, antenatal care, treatment of common diseases, treatment and management of tuberculosis, and HIV/AIDS counselling among curative and preventive services. Although they provide services to outpatients, a few dispensaries may also have a ward for observation. HCs offer similar services to dispensaries with the addition of 24-hour maternity service, emergency care, and casualty admissions in some centres.

Staffing

Both dispensaries and HCs are staffed with nurses and clinical officers. HCs may also have medical doctors

Referral system

Phone numbers for key people involved in the referral processes are registered and displayed in public places, but use varies by provider. Identified transport providers, such as boda bodas (motorbikes) and taxis, are a quick mode of transport to the referral hospital.

O₂ availability

Only HCs have cylinder-based oxygen.

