6.4.2 Pragmatic cluster RCT

Two primary outcomes will be assessed in order to improve the ability to detect a difference between intervention and control arms, given the relatively low occurrence of severe outcomes at primary care level:

- Proportion of children with a severe complication (death or secondary hospitalisation) by Day 7
 - Secondary hospitalisation refers to any delayed hospitalisation (occurring at any point greater than 24 hours after Day 0 consultation) and any hospitalisation occurring without referral. The denominator is all enrolled children

- Proportion of children admitted to hospital within 24 hours of the Day 0 primary care consultation and as a result of a referral
 - This is used as a proxy for 'appropriate referral' of children, as those with severe disease should generally be admitted to hospital. The denominator for this outcome is also all children enrolled in the study, rather than only referred children. This is because the proportion of referred children that are admitted may be high in routine care, in the context of an inappropriately low referral rate. The aim of the intervention is therefore to increase the overall referral rate of children with severe disease. Hospital admission is chosen as the proxy of severe disease rather than using primary care classification of severe disease, as there are inadequacies in the classification of severe disease in routine practice

The trial will be interpreted as positive if either primary outcome is positive with no indication of harm from non-significant outcomes. This will be assessed separately in India and Tanzania and will also be assessed across the two countries for the sub-group of children presenting with cough or difficulty breathing.

We anticipate that we will see a greater effect on the 'appropriate referral' outcome, given that increasing detection and referral of children with severe disease is the focus of the intervention, and that morbidity and mortality among children with severe disease is highly contingent on quality of care at hospital level, which is not the focus of the intervention. Whilst hospital admission is still contingent on factors beyond the remit of the intervention (e.g. on caregiver completion of referral and hospital bed availability), it is not dependent on quality of care during hospital admission.

Secondary outcomes:

- Proportion of children with severe complication (death or secondary hospitalisation) by Day 28

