7.1 Allocation

7.1.1 Sequence generation

The allocation sequence will be generated by a statistician, independent from the study, for all eligible facilities per country, stratified by facility type and location (urban/rural location in Tanzania, district in India). The target number of facilities will be randomly selected from all eligible facilities and allocated to the trial arms. The remaining eligible facilities will be retained in a back-up list for later allocation (using the same procedure) should the need arise (e.g. in case of facility exclusion at study start, or in case of need to add additional clusters in the event of recalculation of sample size).

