5.3 Recruitment

The number of participants enrolled will be presented in a CONSORT flowchart by intervention arm, together with the number of potential participants not recruited due to the child's eligibility

failure, caregiver's refusal to consent or caregiver being underage. Reasons for eligibility failure will be summarised.

Further enrolment figures will be presented by facility type, location and district and a graph will be produced showing monthly and cumulative recruitment.

Additionally, the percentage of eligible children (no. eligible/no. screened) and the percentage of recruited children (no. recruited/no. eligible) will be provided by intervention arm.

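### In Tanzania, council is not pre-specified as a covariate, so a cheap gain in precision, of unknown size, is left to a visual-imbalance rule

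*SAP*

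**What the plan says.** The covariate rule is in SAP 6.2.2: "All models will be adjusted for stratification factors (facility type, location) and baseline variables that are found to be randomly imbalanced across arms". Imbalance is judged by eye, without testing.

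What location means differs by country. For Tanzania, SAP 3.2 has the allocation "stratified by facility type (dispensary/health center) and location (urban/rural) in Tanzania". Protocol 7.1.1 gives the rule for both countries: "stratified by facility type and location (urban/rural location in Tanzania, district in India".

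The Tanzanian setting in Protocol 6.1.2 is "Three councils (Sengerema District Council in Mwanza region, Tanga City Council in Tanga region and Kaliua in Tabora region". So there are three councils in three regions, and council is not among the strata.

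The primary analysis in SAP 6.2.1 is a "random effects logistic regression model with the cluster included as a random effect". The facility is the only random effect. Council differences that the covariates do not capture therefore stay in the between-facility variance.

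**The concern.** A factor that predicts the outcome at facility level adds to the standard error when it is left out of the model, even if the arms happen to be balanced on it. A rule triggered by visible imbalance is therefore no substitute for naming the factor in advance. The baseline summaries described in SAP 5.5 also cover children and caregivers, not council.

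The protocol gives some reason to expect councils to differ. Section 6.4.2 says that "hospital admission is still contingent on factors beyond the remit of the intervention (e.g. on caregiver completion of referral and hospital bed availability"). Both could plausibly vary between three referral areas, although the protocol does not say that they do.

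At stake is precision in Tanzania. Facilities there are large, so between-facility variance dominates the standard error. Recruiting more children per facility does little to reduce it, whereas a facility-level covariate can.

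**Working it through.** **Inputs (SAP 3.4, Protocol 6.6.1).** Severe complication 1.1% against 0.77% (a 30% reduction); hospitalisation 1.5% against 1.95% (a 30% increase); ICC 0.001; m = 1,680 children per facility; 22 facilities per arm; power 80%; alpha 0.05, taken as two-sided because sidedness is not stated. SAP 4.1 starts each primary outcome at alpha 0.025.

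**1. Reproduce the plan's figure.** The two-proportion formula with pooled variance under the null, n = [z(1−α/2)·√(2p̄(1−p̄)) + z(0.80)·√(p1(1−p1) + p2(1−p2))]² / (p1−p2)², gives 13,351 children per arm for severe complication before clustering.

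- Design effect: 1 + (1,680 − 1) × 0.001 = 2.679.
- Clustered size: 13,351 × 2.679 ≈ 35,767.
- Facilities: 35,767 / 1,680 = 21.3, rounded up to 22. This matches the plan.
- Effective size at 22 × 1,680 = 36,960: 36,960 / 2.679 ≈ 13,796. Power is 81.3% at alpha 0.05 and 72.8% at 0.025.
- Hospitalisation: n = 13,141, 21.0 facilities, power 81.9% and 73.5%.

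**2. Share of variance between facilities.** (2.679 − 1) / 2.679 = 0.627, about 63%.

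**3. Effect of adding council.** Let f be the share of between-facility variance that council explains *beyond* facility type and urban/rural. The design effect becomes 1 + 1,679 × 0.001 × (1 − f). The documents give no value for f, so the range is an assumption.

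| f | Design effect | SE ratio | Severe complication, α 0.05 / 0.025 | Hospitalisation, α 0.05 / 0.025 |
|---|---|---|---|---|
| 0 | 2.679 | 1.000 | 81.3% / 72.8% | 81.9% / 73.5% |
| 5% | 2.595 | 0.984 | 82.5% / 74.3% | 83.1% / 75.0% |
| 10% | 2.511 | 0.968 | 83.7% / 75.8% | 84.3% / 76.5% |
| 20% | 2.343 | 0.935 | 86.1% / 78.9% | 86.6% / 79.6% |
| 30% | 2.175 | 0.901 | 88.5% / 82.1% | 89.0% / 82.7% |

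**4. What a given f means in rates.** For three equally common council rates, evenly spaced around p, the half-range is √(1.5·f·ICC·p(1−p)). At p = 1.1% and f = 20% this is 0.18 points, so rates of 0.92%, 1.10% and 1.28%. Here f is the total council share, before any overlap with urban/rural.

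**5. Cost if council explains nothing.** One comparison has 44 facilities. Allowing for arm, facility type and urban/rural leaves about 40 degrees of freedom, and 38 with council. On a t-based calculation, severe-complication power moves from 79.4% to 79.3% at alpha 0.05, and from 69.7% to 69.6% at 0.025. Unrounded, the losses are 0.11 and 0.17 points.

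**6. Unequal facilities.** With the planned mix (one quarter at 4,200 children a year, three quarters at 840) and optimal weighting, severe-complication power at alpha 0.025 is lower throughout: 66.0% at f = 0, 69.0% at 10%, 72.1% at 20% and 75.4% at 30%. The gain from council is about the same as with equal sizes.

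**The case against.** **The gain is unproven.** No passage reports a difference between councils in either outcome. The documents also do not say whether the ICC of 0.001 includes variation between areas. If it describes variation within an area, the plan's ICC holds nothing for council to remove. This stands, and it is why the result is a range that starts at zero.

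**Urban/rural may already do much of the work.** One council is a City Council and another a District Council. Suppose, as an illustration, that the City Council is all urban, the other two all rural, and facility numbers are equal. Take the rates 0.92%, 1.10% and 1.28%, with the City Council at one extreme. The total council variance is 2 × 0.18² / 3 = 0.0216. What urban/rural leaves is (2/3) × 0.09² = 0.0054, a quarter of it. The incremental share falls from 20% to 5%, and the gain at alpha 0.05 from 4.8 points to 1.2. If the City Council has the middle rate, urban/rural absorbs nothing. The documents have no cross-tabulation to settle this, so only the incremental share counts.

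**Council is not shut out.** The second half of the sentence in SAP 6.2.2 could admit it, and SAP 6.2.1 allows clusters to be merged to a higher level, such as district, if the model does not converge. A reader might infer that council can never enter the analysis, and that goes too far. Both routes depend on the data, however, and neither is a plan to adjust for council.

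**Adjusting for the strata is coherent.** It is, and the 80% target is met without council.

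**Conclusion.** Council is not pre-specified in the Tanzanian models, and naming it is a low-cost improvement. On the plan's inputs, with equal clusters, the gain in severe-complication power runs from nil to about 7 points at alpha 0.05 (81.3% to 88.5%) and about 9 points at alpha 0.025 (72.8% to 82.1%) for an incremental share of 0 to 30%. That share is assumed. A value near zero is possible.

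Three stronger readings are not supported:

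- *That power is certainly being lost, or that the estimate is biased.* The loss depends on between-council differences that the documents do not report. Omitting council from a randomised comparison costs precision and does not bias it.
- *That the trial falls short of its target because of this.* On the plan's own basis power is 81.3% without council. The lower figures at alpha 0.025 or with unequal facilities come from those features.
- *That India has the same gap.* SAP 5.3 says "Further enrolment figures will be presented by facility type, location and district", which might suggest that location excludes district. But SAP 3.2 stratifies by facility type "and district (Deoria, Sitapur, Unnao) in India", Protocol 7.1.1 equates location with district there, and both SAP 6.2.2 and Protocol 8.3.1 adjust for the stratification factors.

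**What to change.** Add one sentence to SAP 6.2.2, before outcome data by arm are seen: *In the Tanzanian models, council (Sengerema, Tanga City, Kaliua) is included as a fixed effect, in addition to facility type and urban/rural.*

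The cost is two extra parameters and no new data collection, since each facility's council is known. If council explains nothing, about 0.1 to 0.2 points of power are lost.

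Leave the stratification-factor line of the subgroup list in SAP 6.2.5 unchanged. Council is not a Tanzanian stratum, and another interaction test would add nothing to precision. India's covariates need no change.
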